### **7.4.3 Every 2-Month Overall Survival Monitoring**

Upon completion of the 30-Day SFU visit, subjects will be monitored on an every 2-month visit schedule for survival until death or until study completion. Study completion is defined as the death of at least 70% of subjects or 3 years after the last subject's first dose, whichever occurs earlier.

Only survival status and start of any new anti-cancer therapy will be collected during this period.

Subjects who discontinue study drug without evidence of PD per RECIST v1.1 will have CT scans or MRI every 6 weeks during the survival-monitoring period to determine disease status until PD.

## **8.0 ADVERSE EVENTS (SERIOUS AND NON-SERIOUS)**

### **8.1 Non-serious Adverse Events**

#### **8.1.1 Definition of Adverse Event and Non-serious Adverse Event**

The following definition of adverse event will be used for the study:

Any untoward medical occurrence in a study subject administered a pharmaceutical product and which does not necessarily have to have a causal relationship with this treatment. An adverse event can therefore be any unfavorable and unintended sign (including an abnormal laboratory finding), symptom, or disease temporally associated with the use of a medicinal (investigational) product, whether or not related to medicinal (investigational) product.

This definition includes any abnormalities or anomalies that were not seen at baseline or which worsened during the course of the study, if present at baseline. Disease progression, and events caused by disease progression, will be considered an efficacy endpoint and should not be reported as an AE, even if the event results in hospitalization. Therefore progression of the cancer under study is not considered an adverse event.

A “non-serious” AE is any event that does not meet the definition of “serious adverse event” (SAE) as presented in [Section 8.2](#) below.

#### **8.1.2 Reporting and Treating Non-serious Adverse Events**

It is the responsibility of the Investigator to perform regular assessments for AEs. Subjects will be regularly queried about the occurrence of any AEs and will be monitored throughout the study for reactions to study drug and/or study procedures. The Investigator and clinical staff will record all AEs, whether volunteered by or elicited from the subject, at anytime

during a subject's participation in the study. All events occurring prior to the first dosing will be recorded on the Medical History eCRF, except an SAE leading to exclusion from the trial or as a result of a protocol-specified intervention as described in Section 8.2.2, will be recorded on the Adverse Event eCRF. All AEs occurring at any time after the initiation of the first dose of study drug up to 30 days following the last dose of study drug will be recorded on the Adverse Event eCRF. Adverse events will be recorded according to the CTCAE v4.03 (Appendix 14.4). Adverse events meeting the definition of SAE require additional reporting as described in the following section.

All subjects experiencing an AE will be evaluated by the Investigator and monitored until resolution of the event or until the Investigator deems the event clinically stable and/or at an acceptable level. Unless the event requires hospitalization (SAE), medical treatment will be provided to the subjects at the unit, and treatment medication and/or medical procedures will preferably be provided under the guidance of the treating-Investigator's clinical discretion. All AEs, including clinically significant laboratory abnormalities, will be followed until resolution. Serious adverse events require special reporting in addition to documentation in the eCRF as described in the section on Serious Adverse Events.

It is the Investigator's responsibility to provide his/her assessment of the relationship of the event to the study drug and the severity of the event using the following scales:

- Relationship
  - No (unrelated, not related, no relation) – The time course between the administration of study drug and the occurrence or worsening of the AE rules out a causal relationship and another cause (concomitant drugs, therapies, complications, etc.) is suspected
  - Yes – The time course between the administration of study drug and the occurrence or worsening of the AE is consistent with a causal relationship and no other cause (concomitant drugs, therapies, complications, etc.) can be identified
- Severity

The severity of all AEs should be graded according to the CTCAE v4.03. These criteria can be found at <http://ctep.cancer.gov/reporting/ctc.html>. For those AEs not listed in the CTCAE, the following grading system should be employed:

- Mild (CTCAE Grade 1): Transient symptoms, awareness of sign/symptom, but easily tolerated and no interference with subject's daily activities
- Moderate (CTCAE Grade 2): Marked signs/symptoms that interfere with subject's usual activities, but still acceptable
- Severe (CTCAE Grade 3): Incapacitating signs/symptoms which cause considerable interference with the subject's daily activities, unacceptable

- Life-threatening (CTCAE Grade 4): Life-threatening or disabling adverse event
- Death (CTCAE Grade 5): Death-related adverse event. See CTCAE Guidelines for assigning Grade 5.

## 8.2 Serious Adverse Events

### 8.2.1 Definition of Serious Adverse Event

The following definition of SAE applies for the study:

An SAE is defined as any AE occurring at any dose that results in any of the following outcomes:

- Death
- Life-threatening AE
- Inpatient hospitalization or prolongation of existing hospitalization
- Persistent or significant disability/incapacity
- Congenital anomaly/birth defect

Important medical events that may not result in death, be life threatening, or require hospitalization may be considered an SAE when, based upon appropriate medical judgment, they may jeopardize the subject and may require medical or surgical intervention to prevent one of the outcomes listed in this definition. A life-threatening AE is any AE that places the subject or subjects, in the view of the Investigator, at immediate risk of death from the reaction as it occurred (eg, it does not include a reaction that, had it occurred in a more severe form, might have caused death).

In addition to the above criteria, adverse events meeting either of the below criteria, although not serious per ICH definition, are reportable to the Sponsor in the same timeframe as SAEs in order to meet certain local requirements.

Therefore, the following events are considered serious by the Sponsor for collection purposes:

- Is a new cancer (that is not a condition of the study)
- Is associated with an overdose

### 8.2.2 Reporting and Treating Serious Adverse Events

An AE that is serious (SAE) requires additional detailed reports and follow-up. The content of these detailed reports must address the Investigator's estimate of causality and must provide the information specified in the SAE Report Form and International Conference on Harmonisation (ICH) guidelines, in so far as is possible.

For the time period beginning when the consent form is signed until treatment enrollment, any serious adverse event, or follow up to a serious adverse event, including death due to any cause other than progression of the cancer under study, that occurs to any subject must be reported within 24 hours to the Sponsor if it causes the subject to be excluded from the trial, or is the result of a protocol-specified intervention, including but not limited to discontinuation of usual therapy, diet, or a procedure.

For the time period beginning at treatment enrollment through 90 days following cessation of treatment, or 30 days following cessation of treatment if the subject initiates new anticancer therapy, whichever is earlier, any serious adverse event, or follow up to a serious adverse event, including death due to any cause other than progression of the cancer under study, whether or not related to the Sponsor's products, must be reported within 24 hours to the Sponsor.

Additionally, any serious adverse event, considered by an Investigator who is a qualified physician to be related to the Sponsor's products that is brought to the attention of the Investigator at any time following consent through the end of the specified safety follow-up period specified in the paragraph above, or at any time outside of the time period specified in the previous paragraph, also must be reported immediately to the Sponsor.

All subjects with serious adverse events must be followed up for outcome.

Following is the safety contact information for reporting serious adverse events worldwide:

Safety Contact Information  
SAE [contact]  
[contact]  
E-mail: [[contact]](mailto:[contact])

The Investigator will be requested to supply detailed information regarding the event. All serious and unexpected AEs/SAEs must also be reported to the reviewing IEC/IRB as per specific requirements and a copy of that report must be retained at the investigative site and filed in the Investigator Site File.

Death due to any cause occurring >30 days after the last dose of study drug during the survival-monitoring period will not be reported as an adverse event. Disease progression will not be reported as an AE/SAE.

Each Investigator is responsible for reporting adverse events observed with concomitant medications per his/her region's respective regulatory guidelines.

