12.2 Adverse Events

All subjects will be assessed regularly for the potential occurrence of adverse events (AEs) from the date of informed consent to 30 days after the last dose of study drug. The incidence of treatment-emergent AEs (TEAEs) will be summarized and tabulated using MedDRA (version 18.1), by System Organ Class (SOC) and Preferred Term (PT). A TEAE is defined as an AE that first occurs or worsens in severity on or after the first dose of any study drug and within 30 days after the last dose of any study drug.

The National Cancer Institute Common Terminology Criteria for Adverse Events (CTCAE) (Version 4.03) will be used to grade both clinical and laboratory AEs. A subject with several occurrences of the same AE will be counted once and classified by the most severe occurrence. AEs with missing severity ratings will be classified as having unknown severity.

An overview summary of AEs will be produced, which will include counts and percentages of subjects with any AEs and Grade III/IV AEs, AEs and Grade III/IV AEs related to study treatment, SAEs, SAEs related to study treatment, fatal SAEs, infusion reactions, AEs leading to dose delayed, dose reduced, and dose withdrawn for Imprime PGG, AEs leading to dose delayed and dose withdrawn for pembrolizumab, and AEs leading to study treatment discontinuation. AEs related to study treatment will be further categorized as AEs related to Imprime PGG and/or pembrolizumab, Imprime PGG only, pembrolizumab only, and both Imprime PGG and pembrolizumab.

A treatment-related AE is defined as an AE for which the investigator classifies the relationship to study treatment as “Yes”. A worst-case scenario approach will be taken to handle missing data, i.e. AEs related to study treatment will include events with the relationship to study treatment as ‘YES’ or missing. Adverse event data will be reviewed periodically to identify infusion reactions, new cancers, and events related to pembrolizumab overdose ($\geq 1000\text{mg}$).

The AE summary tables will use the following algorithms for counting subjects:

- **Preferred term rows:** each subject is counted once within each unique preferred term at the maximum grade. For example, if a subject has two headaches, the subject is counted only once under the preferred term “Headache”. Subjects experiencing the same AE preferred term several times with different grades will only be counted once with the maximum grade.

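### Protocol 8.2.2 gives two incompatible rules for reporting a non-progression death on days 31 to 90 after treatment in a subject who has not started new anticancer therapy

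*Protocol*

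**What the plan says.** Protocol 8.2.2 sets the SAE reporting period, which opens at enrollment for treatment and runs "through 90 days following cessation of treatment, or 30 days following cessation of treatment if the subject initiates new anticancer therapy, whichever is earlier". Within it, any SAE goes to the sponsor within 24 hours, "including death due to any cause other than progression of the cancer under study, whether or not related" to the study products. SAEs that the investigator considers related carry a further duty with no time limit: those that come to light "or at any time outside of the time period specified in the previous paragraph, also must be reported immediately". SAE reports must address causality and "must provide the information specified in the SAE Report Form".

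The same section closes with the opposite instruction for late deaths, whatever their cause: those "occurring >30 days after the last dose of study drug during the survival-monitoring period will not be reported as an adverse event".

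Protocol 8.2.1 ties the two terms together: "An SAE is defined as any AE occurring at any dose that results in any of the following outcomes", with death first on the list of outcomes.

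SAP 12.3 takes over the 90-day period (30 days with new therapy) as the treatment-emergent period for SAEs and plans a subject-level listing of fatal SAEs. SAP 12.5 summarises all deaths by primary cause and by whether they fell within or beyond 30 days of the last dose.

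**The concern.** Safety of the combination is listed with the primary objectives in Protocol 3.1. Protocol 5.2.1.2.2 itself warns that immune-related toxicity can appear months after pembrolizumab has stopped, so the contested days are days on which a late treatment-related death is plausible.

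A site that applies the reporting-period paragraph will file a fatal SAE with a causality assessment. A site that applies the closing sentence will record only the death. The SAP 12.3 fatal-SAE listing claims a 90-day window and would then be complete for some sites and cut at 30 days for others. The death summary in SAP 12.5 gives time and primary cause but plans no summary by relationship to treatment, so it does not replace the missing assessment. The SAP rule that counts a missing relationship as related (SAP 9.1.2 and 12.3) does not help either, because it acts only on events that were entered.

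**Working it through.** The plan gives no figure to reproduce. The check is a comparison of rules, followed by a rough size.

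**1. One case under each rule.** Take a non-progression death 60 days after the last dose, with no new anticancer therapy.

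| Text | Result |
|---|---|
| Protocol 8.2.2, reporting period | SAE, report within 24 hours |
| Protocol 8.2.2, closing sentence | not reported as an adverse event |
| SAP 12.3 | inside the 90-day period, belongs in the fatal-SAE listing |
| SAP 12.5 | counted as a death, in the class beyond 30 days |

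**2. Where the rules agree and where they do not.**
- Death due to progression: both rules exclude it. No conflict.
- New anticancer therapy started: the general period also ends at day 30. The rules agree, except for a related SAE, which stays reportable at any time.
- Related death after day 90: the any-time duty applies, and the closing sentence excludes it. Conflict.
- Non-progression death on days 31 to 90, no new therapy: conflict, whether or not it is related.

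**3. Does the survival-monitoring condition separate the rules?** Protocol 7.4.2 puts the safety follow-up visit within 4 weeks of the end of dosing with a window of -7 days, so at about day 28 - 7 = 21 to day 28. Protocol 7.4.3 starts survival monitoring once that visit is done. Days 31 to 90 therefore lie inside survival monitoring, and the condition separates nothing.

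**4. Length of the overlap.** 90 - 30 = 60 days, which is 60/90 = 67% of the post-treatment part of the SAE period. This treats last dose and cessation of treatment as the same day. It is a span of time and says nothing about the share of data lost.

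**5. Illustrative number of deaths, TNBC.** Inputs: median OS 8.9 months (95% CI 7.2 to 11.2) and median PFS 2.0 months, from the KEYNOTE-086 Cohort A results in Protocol 4.3.1; 41 subjects from Protocol 2.1; 30.4375 days per month from SAP 9.2.2. Assumptions: constant hazard, 2.0 months on treatment, and 5 to 20% of deaths in the interval being non-progression deaths without new therapy. The last range does not come from the documents.
- Hazard: ln 2 / 8.9 = 0.0779 per month.
- Probability of death over 60 days: 1 - exp(-0.0779 x 60/30.4375) = 0.142.
- Alive 30 days after 2.0 months of treatment: exp(-0.0779 x (2.0 + 30/30.4375)) = 0.793.
- Deaths in the interval: 41 x 0.793 x 0.142 = 4.6. Under both rules: 5% gives 0.2 and 20% gives 0.9.
- If all 41 are at risk: 41 x 0.142 = 5.8, which gives 0.3 to 1.2.
- Across the OS confidence interval, the version with 2.0 months on treatment gives 0.2 to 1.1.

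Protocol 4.3.1 gives no survival figure for melanoma, so that cohort is not estimated.

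**The case against.** The best defence is that the two sentences address different things. The closing sentence speaks only of an adverse event, while the next one, on progression, speaks of an AE or SAE, so the drafter may have meant different channels. Protocol 8.1.2 also says that SAEs get special reporting in addition to the eCRF. On this reading the causal event is reported as an SAE, and the closing sentence only stops sites from entering death itself as an event term. That may have been the intention, but the text does not carry it. Every SAE is an AE by Protocol 8.2.1, and the reporting-period paragraph names death itself among the things to report.

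Other parts of the defence stand, and they limit the point. A reader might infer more than the documents support:
- **That SAP 12.2 and 12.3 contradict each other.** SAP 12.2 assesses AEs "from the date of informed consent to 30 days after the last dose of study drug" and defines treatment-emergent AEs as those "on or after the first dose of any study drug and within 30 days after the last dose of any study drug", yet its overview table has SAE and fatal-SAE rows. But SAP 12.3 sets its period for SAEs in general, and applying it to those rows is the natural reading. Only a cross-reference is missing.
- **That late SAEs have no route into the data.** The 30-day eCRF limit stands in Protocol 8.1.2, which concerns non-serious events and refers SAEs to the next section. Protocol 7.4.3 limits what survival contacts collect, but it does not cancel event-driven SAE reporting.
- **That the differing anchors make the overlap longer than 60 days.** This would require cessation of treatment to mean the end of the last cycle. Protocol 7.4.1 uses the end of the cycle to time a visit and does not define cessation.
- **That deaths are lost to the trial.** They are not: OS and the SAP 12.5 summary and listing keep them.

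**Conclusion.** The contradiction is real and sits within one section. For a subject who has not started new anticancer therapy, Protocol 8.2.2 both requires and rules out the reporting of a non-progression death on days 31 to 90. For related deaths the clash has no end date.

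The consequence is narrow. The primary response-rate analysis and OS do not change. At risk is the fatal-SAE record with its causality assessment, and consistency between sites in the SAP 12.3 listing. The expected number is about one TNBC death or fewer (0.2 to 1.2). That rests on a constant hazard taken from pembrolizumab monotherapy, a short time on treatment (treatment may continue past first progression), and an assumed 5 to 20% share. One such death would be 1/41 = 2.4% of the TNBC cohort or 1/29 = 3.4% of the melanoma cohort, so a single missing record can be visible in the safety results. The text should be corrected because the correction is cheap and the record concerns a primary objective; the expected number of deaths is not the reason.

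**What to change.** Reconcile the text of Protocol 8.2.2:
1. Limit the closing sentence to deaths due to progression of the cancer under study, or deaths after the section's own SAE reporting period has closed.
2. State there that the any-time duty for related SAEs still applies.
3. Choose one anchor date, last dose or cessation of treatment, define it, and use it in Protocol 8.2.2 and SAP 12.3.

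Two matching clarifications: say in Protocol 8.1.2 that SAEs are recorded for the 8.2.2 period, and cross-refer the SAE and fatal-SAE rows of the SAP 12.2 overview to the SAP 12.3 period.

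The cost is a few sentences of protocol wording, one anchor definition and one cross-reference in the SAP. No visit, procedure or new questioning at survival contacts is needed. SAP 5.1 describes the Stage 1 interim analysis as already done, so the corrected wording has to be sent to sites in a trial under way.

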### **8.3 Definition of an Overdose for This Protocol and Reporting of Overdose**

For purposes of this trial, an Imprime PGG overdose will be defined as any Imprime PGG dose > 6 mg/kg (50% increase).

For purposes of this trial, a pembrolizumab overdose will be defined as any pembrolizumab dose  $\geq$  1000 mg (5 times the dose).

There have been no known reports of overdose of Imprime PGG. No specific information is available on the treatment of overdose of either Imprime PGG or pembrolizumab. In the event of overdose, study medication should be discontinued and the subject should be observed closely for signs of toxicity. Appropriate supportive treatment should be provided if clinically indicated.

All reports of overdose with and without an adverse event must be reported within 24 hours of the Investigator's knowledge of the event to the Sponsor.

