### 2.1 Trial Design

The study will incorporate Simon's optimal 2-stage design with sample size fixed at 12 subjects each in Stage 1 for advanced melanoma and for Triple Negative Breast Cancer (TNBC) subjects. The safety criterion of  $\leq 4$  (or  $\leq 33\%$ ) subjects with Grade 3/4 adverse events in Cycle 1 within either tumor type must be met in order to proceed to Stage 2. The starting dose is 4 mg/kg for Imprime PGG. In the event there are a total of  $> 4$  (or  $> 33\%$ ) of subjects with Grade 3/4 adverse events in Cycle 1, the dose of Imprime PGG will be reduced to 2 mg/kg, and Stage 1 will be repeated at a dose of 2 mg/kg with an additional cohort of n=12 subjects. For the dose that meets the safety criterion in Stage 1, at least 1 response in melanoma subjects and 1 response in TNBC subjects amongst the 12 subjects within each tumor type must be observed in order to proceed to Stage 2.

Stage 2 will enroll an additional 17 subjects with melanoma, and 29 subjects with TNBC. For the dose that meets the Stage 1 safety criterion, success will be declared if at least 4 amongst the total of up to 29 subjects with melanoma, and 5 amongst the total of up to 41 subjects with TNBC achieve an objective response.

The study population will be those having failed front-line therapy, defined as any treatment regimen or regimens used specifically in the treatment of metastatic disease. Refer to [Section 5.1 on Entry Criteria](#) for the study-specific requirements.

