## **3. Dose Reduction**

If a subject experiences an infusion reaction despite having been administered premedication and despite the infusion time being lengthened, the PI may re-challenge the subject at the next visit by dose reducing the Imprime PGG to 2 mg/kg.

All attempts should be made to ameliorate Grade 3/4 infusion reactions by the Investigator following the 3 recommendations provided above sequentially.

In Stage 1, any Grade 3/4 infusion reactions mitigated by these actions and either resolving or decreasing to Grade 1/2, if this mitigation occurs within Cycle 1 and the Grade 3/4 infusion reaction does not recur in Cycle 2, will not be counted towards the total of > 4 or 33% of Grade 3/4 adverse events which require halting the study in Stage 1 for each individual indication. Only Cycle 1 Grade 3/4 infusion reactions (or those which recur in Cycle 2) will be counted towards the total which would halt advancement to Stage 2.

- In the event there are a total of > 4 or 33% of Grade 3/4 adverse events in Stage 1 which were unable to be ameliorated by the sequential recommendations above, the dose of Imprime PGG will be reduced to 2 mg/kg.
- Stage 1 will be repeated with an additional cohort of n=12 subjects at the reduced dose of 2 mg/kg. Toxicity at the dose of 2 mg/kg will be assessed in this additional Stage 1 cohort in the same manner as was done for the initial dose of 4 mg/kg, with the identical sequential recommendations for any observed infusion reactions.
- Advancement to Stage 2 will be halted if there are > 4 or 33% of Grade 3/4 adverse reactions. Otherwise, subjects will proceed to Stage 2 with all subjects at the new, reduced dose of 2 mg/kg.

Note that continuation onto Stage 2 requires a demonstration of at least 1 or 2 objective responses in subjects with melanoma or TNBC, respectively, in addition to meeting the adverse event requirements detailed above, at either Imprime PGG dose of 4 mg/kg or 2 mg/kg. Please refer to the [Trial Diagram](#) in [Section 2.2](#) for a schema of the study flow from start to end.

In general, any Grade 4 non-infusion or non-hematological AE will lead to the withdrawal of the subject from treatment. A dosing delay of up to 3 weeks is allowed in case of Grade 3 non-hematological AEs to reduce toxicity to baseline or Grade 0-1. Dose levels will be adjusted individually for each study drug.

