All subjects will receive Imprime PGG and pembrolizumab. Imprime PGG will be administered IV at a dose of 4 mg/kg over a 2-hour infusion time period on Day 1, Day 8, and Day 15 of each 3-week cycle for subjects at stage 1. If Stage 1 proceeds without safety concerns necessitating a second cohort at 2 mg/kg, Imprime PGG will be administered to the Stage 2 subjects at a dose of 4 mg/kg IV over a 2-hour infusion time period on Day 1, Day 8, and Day 15 of each 3-week cycle. If enrollment into an additional cohort for 2 mg/kg in Stage 1 is required and dosing proceeds to Stage 2, Imprime PGG will be administered in Stage 2 at a dose of 2 mg/kg IV over a 2-hour infusion time period on Day 1, Day 8, and Day 15 of each 3-week cycle. The pembrolizumab fixed dose of 200 mg will be administered IV over 30 minutes on Day 1 of each 3-week treatment.

Subjects will be dosed until disease progression, death, 2 years of treatment or study completion, whichever occurs first. After treatment discontinuation, subjects will be monitored every 2 months for survival until death or study completion. Study completion is defined as the death of at least 70% of subjects or 3 years after the last subject's first dose, whichever occurs earlier.

Discontinuation of treatment may be considered for subjects who have attained a confirmed CR, who have been treated for at least 24 weeks, and who had at least 2 treatments with study medications beyond the date when the initial CR was declared. Subjects who then experience radiographic disease progression may be eligible for up to 1 year of additional treatment with Imprime PGG + pembrolizumab at the discretion of the Investigator if:

- No cancer treatment was administered since the last dose of pembrolizumab
- The subject meets the safety parameters listed in the Inclusion/Exclusion criteria
- The trial is open

Subjects will resume therapy at the same dose and schedule at the time of initial discontinuation. Response or progression in this resumed course of therapy will not count towards the ORR of the primary endpoint in this trial.

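### SAP 12.2 reviews and lists overdose for pembrolizumab only, and Protocol 8.3's single > 6 mg/kg limit triggers no 24-hour report when a subject individually reduced to 2 mg/kg is given 4 mg/kg in error

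*Protocol*

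**What the plan says.** Protocol 8.3 sets one limit for the whole trial: "an Imprime PGG overdose will be defined as any Imprime PGG dose > 6 mg/kg (50% increase"). For pembrolizumab the limit is 1000 mg or more, described as five times the dose. Two actions follow from the definition: "All reports of overdose with and without an adverse event must be reported within 24 hours", and "study medication should be discontinued and the subject should be observed closely for signs of toxicity". Protocol 8.2.1 adds any adverse event that "Is associated with an overdose" to those collected as serious. Protocol 8.5 makes a symptomless overdose of either product an event of clinical interest, reportable within 24 hours, and refers back to 8.3 for the definition.

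A subject can be at 2 mg/kg by two routes.

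- **By cohort.** If more than 4 Stage 1 subjects have Grade 3/4 events in Cycle 1, Protocol 2.1 says "the dose of Imprime PGG will be reduced to 2 mg/kg, and Stage 1 will be repeated at a dose of 2 mg/kg". If that cohort passes, SAP 4 says "Imprime PGG will be administered in Stage 2 at a dose of 2 mg/kg IV".
- **Individually.** When premedication and a slower infusion have both failed to prevent a reaction, Protocol 5.2.1.2.1 (Dose Reduction) says that "the PI may re-challenge the subject at the next visit by dose reducing the Imprime PGG to 2 mg/kg".

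SAP 12.2 mentions overdose twice, once for the periodic review of adverse event data and once for a separate listing. Both times it names pembrolizumab alone. SAP 12.1 lists, for each Imprime PGG infusion, the dose level, the weight-based total and the total dose received.

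**The concern.** The first gap is one of scope. The protocol asks for overdose of both products to be captured, but a programmer following SAP 12.2 literally would review and list overdose events for the licensed drug and not for the investigational one. This holds at either Imprime PGG dose level.

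The second gap concerns the 8.3 limit. Its description as a 50% increase ties it to an assigned dose of 4 mg/kg. For a subject cut to 2 mg/kg because infusion reactions persisted despite premedication and a longer infusion, 4 mg/kg is the dose that caused the trouble. Giving it again in error is not an overdose under 8.3. The error then needs no 24-hour report, is not an event of clinical interest, and carries no 8.3 instruction to observe closely. Unless it led to an event serious in its own right, the sponsor would learn of it only later, from routine data.

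**Working it through.** **Part 1: the SAP against the protocol.**

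- *Covered by the protocol:* both drugs, in 8.2.1 (adverse events associated with an overdose), 8.3 (both limits) and 8.5 (symptomless overdose of either product).
- *Covered by SAP 12.2:* pembrolizumab only, in both the review and the listing.
- *Other routes for Imprime PGG:* the all-AE listing (SAP 12.2), the SAE listing (SAP 12.3, since 8.2.1 collects overdose-associated events as serious) and the infusion listing (SAP 12.1). The data exist, but none of these displays is specified to identify an Imprime PGG overdose. A listing built on adverse events may also miss a symptomless overdose of either drug.

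**Part 2: the limit relative to the assigned dose.**

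Inputs: limit 6 mg/kg (Protocol 8.3); dose levels 4 and 2 mg/kg (Protocol 2.1 and 5.2.1.2.1); 70 kg worked example (Appendix 14.1); pembrolizumab limit 1000 mg (8.3) and dose 200 mg (5.2.1.1).

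1. The plan's own figures reproduce. Limit / assigned dose = 6/4 = 1.5, a 50% increase. For pembrolizumab, 1000/200 = 5.
2. At 2 mg/kg: 6/2 = 3.0, a 200% increase. Because the rule is strictly above 6, a dose of exactly three times the assigned level is still not an overdose.
3. The error of interest: 4/2 = 2.0 times the assigned dose, below the limit.
4. A 50% margin at 2 mg/kg would be 1.5 x 2 = 3 mg/kg. This is the margin proposed here; the protocol does not state it.

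At 70 kg:

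| Dose | mg/kg | mg |
|---|---|---|
| Assigned | 2 | 2 x 70 = 140 |
| Proposed reporting limit | > 3 | > 3 x 70 = 210 |
| 4 mg/kg given in error | 4 | 4 x 70 = 280 |
| Limit in 8.3 | > 6 | > 6 x 70 = 420 |

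**Would preparation checks catch it?** Only partly. Table 6 and Table 14.1 give the same volume, infusion time and rate for both dose levels within each weight band, so these do not tell the bags apart. The 4 mg/kg bag is 280/500 = 0.56 mg/mL, under the 0.8 mg/mL maximum of Protocol 10.5, so that maximum does not flag it. The vial count can: 280/50 rounds up to 6 of the 50-mL vials, against 140/50 rounded up to 3, the number stated for 2 mg/kg.

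**Whom does the intolerance argument fit?** A repeat 2 mg/kg Stage 1 cohort is an additional 12 subjects, and exclusion criterion 10 bars previous Imprime PGG exposure. Those subjects, and any Stage 2 subjects at 2 mg/kg, are therefore new to the drug and have not failed 4 mg/kg. The argument fits only subjects reduced individually.

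**The case against.** The strongest objection is that 8.3 sets a deliberate absolute ceiling. It binds every subject, including those at 2 mg/kg. Doses of 6 mg/kg were used in earlier studies, namely the single-dose healthy-volunteer study (Protocol 4.1.1.1.1) and the colorectal study CRC0713 (4.1.1.2.1), and 4 mg/kg is this trial's starting dose. A three-fold margin at 2 mg/kg is tighter than the five-fold margin that the same section accepts for pembrolizumab. Nor is the event lost: adverse events are recorded, serious ones go to the sponsor within 24 hours, noncompliance is documented (Protocol 5.8.1), important deviations are listed (SAP 10.2), and SAP 12.1 shows the dose received.

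Most of this stands. It defeats three stronger readings that a reader might infer:

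- *That 8.3 contains an arithmetic error.* It does not; 50% is right at 4 mg/kg.
- *That 2 mg/kg subjects have no overdose rule.* They have the > 6 mg/kg ceiling. What they lack is a limit relative to their own dose.
- *That whole 2 mg/kg cohorts consist of subjects who could not tolerate 4 mg/kg.* They are Imprime-naive. The Stage 1 trigger in Protocol 2.1 also counts Grade 3/4 events without requiring that they be drug-related. Head counts of such cohorts therefore do not measure this risk.

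Two things are left. None of the alternative routes except SAE reporting carries a 24-hour clock, and a ceiling based on earlier exposure does not address someone who has just reacted to 4 mg/kg. The objection also does not explain why SAP 12.2 omits the investigational drug. The display lists that the SAP places in 15.1 and 15.2 are not in the available text, so the point rests on the 12.2 wording alone.

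**Conclusion.** The point holds as a minor, optional improvement to safety capture.

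The SAP 12.2 gap is plain from the text and does not depend on anyone receiving 2 mg/kg. The events remain in general listings; what is missing is their targeted review and listing.

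The 8.3 gap is narrower. It concerns subjects individually reduced to 2 mg/kg who then receive 4 mg/kg in error, at 2.0 times the assigned dose against a cut-off of 3.0 times. It assumes that such a subject is still assigned to 2 mg/kg at that infusion; the dose-reduction text does not say whether a planned return to 4 mg/kg is allowed. Neither the number of such reductions nor a misdosing rate is given, so no expected count can be calculated, and it may be zero.

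Nothing here bears on the response rate, sample size, type I error or power, and neither gap should be read as weakening the efficacy result.

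**What to change.** 1. **SAP 12.2:** in the periodic review and in the separate listing, refer to Imprime PGG or pembrolizumab overdose as defined in Protocol 8.3.
2. **SAP 12.1 data:** derive a flag so that symptomless overdoses are found. For Imprime PGG, flag total dose received divided by the body weight used for dosing when it is > 6 mg/kg, and separately when it is > 3 mg/kg in a subject assigned to 2 mg/kg. For pembrolizumab, flag dose received of 1000 mg or more. Take the assigned level from the cohort and dose-reduction record, because the dose-level field in the infusion listing may already show the dose given in error.
3. **Protocol 8.3:** keep > 6 mg/kg as the overdose definition, with its present consequences for discontinuation and seriousness. Add one sentence requiring a 24-hour report and close observation for any Imprime PGG dose more than 50% above the assigned level (> 3 mg/kg) in a subject assigned to 2 mg/kg.

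The cost is two phrases and a derived flag in the SAP, one sentence in the protocol, and a few extra 24-hour reports. Because the overdose definition does not move, no further adverse events become serious by rule and no further discontinuations are required. The change therefore does not by itself affect subject replacement (Protocol 5.9) or the Evaluable population (SAP 6).
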